Based on estimates from the Division of Pediatric Surgery, PCH performs approximately 1000 laparoscopic appendectomies annually. Approximately one-third of these appendectomies (300) are perforated; about 10%-20% of these 300 perforated patients (30-60) will develop a post-surgical abscess treated with a percutaneous drain and IV antibiotics.

Screening - The study population is comprised of patients who, upon admission, are diagnosed with perforated appendicitis and who, after laparoscopy, form an abscess (while still in hospital or discharged and then readmitted with abscess), and are treated with percutaneous drainage and IV ceftriaxone/metronidazole or other broad spectrum antibiotic equivalent per hospital standard of care. Screened patients will be assigned a screening ID, which will be maintained in a screening log.

Randomization - Once eligibility for study inclusion is determined at the time of drainage, the patient will be consented by the principal investigator or sub-investigator and assigned a study number. A block randomization strategy will be used based on a random number generator and applied after consent by site to assign patients to either the control (8-day) or experimental (4-day) arm of the study. All patients will be randomly assigned by patient study numbers. A current randomized trial underway at Phoenix Children's Hospital requires photography to confirm a diagnosis of perforation (IRB 17-011). We propose to follow the same approach for verifying perforated appendicitis across WSPRC institutions in this study. When possible, the hole or feces will be

IRB#: 17-055

Title: A prospective randomized trial of antibiotic duration in post-appendectomy abscess

PI: [name]

Col's: [name], [name]; [name]; [name]; [name]; [name]; [name]; [name] [name]; [name]; [name].

photographed. If not, "hole," "feces/stool in the abdomen," or other note describing perforation will need to be specifically described in the operative report. The two study arms will include some patients with abscess that has been confirmed though CT or ultrasound as part of standard of care prior to study participation. We will include CT/ultrasound results as part of data collection.

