Antibiotic regimen - All post-laparoscopic abscess patients will receive the standard of care for antibiotic therapy—IV ceftriaxone/metronidazole or other broad spectrum antibiotic equivalent—until afebrile (38.5° C) and tolerating food for 24 hours (i.e., without vomiting). CBC panels are also standard of care and may be drawn multiple times during the patient's stay. Standard of care at discharge includes prescribed oral, empiric, antibiotic therapy (PO), such as ampicillin/clavulanate or other broad spectrum antibiotic. The choice and the duration of broad spectrum antibiotic prescription are at the surgeon's discretion.

In this study, all patients will be treated with the hospital standard of care and receive in-patient treatment for abscess until afebrile and tolerating food for 24 hours. After percutaneous drainage of the abscess, the patient will be randomly assigned to receive either an 8-day regimen (arm A) or a 4-day regimen (arm B) of antibiotics (Diagram 1). Patients will remain on IV ceftriaxone/metronidazole or other broad spectrum antibiotic equivalent until afebrile and tolerating food for 24 hours. Patients will complete their assigned 4- or 8-day regimen with oral ampicillin clavulanate or other broad spectrum antibiotic equivalent. If patients are not afebrile at the completion of their assigned regimen, prescribing an extended course of antibiotics is at the discretion of the treating surgeon. A prescribed oral course of antibiotics may be finished in the hospital or at home if patient is discharged.

Ampicillin and clavulanate have been safely utilized in previous pediatric research.^{5,10,14,11} These antibiotics have demonstrated clinical equivalence in both retrospective studies and prospective trials.^{9,11} This randomized trial is the first to address duration of antibiotic treatment in pediatric patients diagnosed with perforated appendicitis and who form a post-laparoscopic abscess. Pediatric patients who are allergic to ampicillin will be prescribed another broad-spectrum antibiotic (e.g., gentamycin/clindamycin or ciprofloxacin) at the discretion of the treating surgeon.

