Two arms are proposed for the study following the protocol implemented for adults in a recent randomized trial.²¹ In the control arm, patients will be treated with an 8-day course of antibiotics, and in the experimental arm, patients will be treated with a 4-day course of antibiotics. The randomized trial should control for all confounding effects. In addition,

IRB#: 17-055

Title: A prospective randomized trial of antibiotic duration in post-appendectomy abscess

PI: [name]

CoI's: [name], [name]; [name]; [name]; [name]; [name]; [name]; [name] [name]; [name]; [name].

we will collect clinical data on the pre-operative, peri-operative and post-operative antibiotic treatment and number of days on antibiotic therapy prior to discharge to manage this potential confounder *post hoc*.

There is a low probability of study attrition or loss to follow-up. As the primary treatment provider in a study with a short (30-day) follow-up period for readmission, we do not expect significant attrition. Follow-up will entail tracking all patients from the initial study who return to the hospital for complications related to the procedure within 30 days of discharge. All complications, including those requiring readmission, will be included in the follow-up. All study patients will be assessed for primary and secondary clinical outcomes. Complications associated with surgically treated acute appendicitis based on the National Surgery Quality Improvement Program criteria (available at <http://nsqip.healthsoftonline.com/hsi/>) include (1) wound infection, (2) abscess, (3) post-discharge small bowel obstruction, (4) hernia, (5) length of hospital stay of greater than 4 days, and (6) death.

[figure not shown]
IRB#: 17-055

Title: A prospective randomized trial of antibiotic duration in post-appendectomy abscess

PI: [name]

CoI's: [name], [name]; [name]; [name]; [name]; [name]; [name]; [name] [name]; [name]; [name].

Diagram 1: Treatment arms for randomized trial of an 8-day antibiotic treatment vs. 4-day treatment of post-laparoscopic abscess formation in pediatric complicated (perforated) appendicitis.

* If febrile after assigned course of antibiotics (i.e., 8 days or 4 days) is completed, extended antibiotic treatment will be up to the treating surgeon.

†Patient may be discharged before 8- or 4-day course is completed and may finish antibiotics at home.

IRB#: 17-055

V5 9/25/2019

IRB#: 17-055

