Col's: [name], [name]; [name]; [name]; [name]; [name]; [name]; [name] [name]; [name]; [name].

It is estimated that it will take about 6 years for PCH to fill the study arms; interim analysis will be performed when study cohorts are half-filled. In order to complete this and other planned pediatric appendicitis studies more quickly, we are planning to add other study sites through the Western Surgical Research Consortium. The multisite approval process will be facilitated by Streamlined Multisite Accelerated Resources for Trials (SMART) IRB certification. With participation from the nine hospitals in the Western Surgical Research Consortium, we would expect to fill the trial cohorts in approximately 2 years.

C.4. Data Analysis Plan

The study will describe patient and clinical characteristics related to laparoscopy among study cohorts (e.g., age, BMI, gender, maximum temperature upon admission, diarrhea at presentation, duration of symptoms, and white blood cell count); patient recovery and abscess formation (e.g., time to abscess, abscess size if available, time to regular diet, and LOS after the drainage); primary clinical outcome (readmission); and secondary clinical outcomes (LOS, total visits after discharge, post-drainage occurrence of abscess, and post-drainage secondary infection).

All data will be described using descriptive statistics, including means, standard deviation, and proportions. Differences among treatment cohorts and on clinical outcomes will be assessed using parametric and non-parametric tests as appropriate. Factors confounding outcomes will be identified *a priori* from research and empirically via correlational analysis for continuous measures or through non-parametric techniques for discrete variables with a Bonferroni correction for multiple comparisons among families of statistical tests. Binomial logistical regression will also be used where appropriate. Unadjusted odds ratios will be used to identify variables of interest and confounding effects for discrete dependent variables of interest. Adjusted odds ratios will be used to compare differences among study cohorts and covariates (e.g., age, gender, white blood cell count, and BMI), interactions, and confounders as appropriate. Statistical significance will be defined as an alpha of 0.05, with two-sided alternative hypothesis and a Bonferroni correction for multiple comparison. Data analysis will be performed using SPSS and R.

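### C.1 treats antibiotic days up to discharge as a potential confounder without separating exposure before drainage from exposure after it, and C.4 does not limit adjusted arm comparisons to variables fixed before randomisation (minor)

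*Combined protocol and SAP*

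**What the plan says.** **Timing of randomisation.** C.1 (Randomization) places eligibility and consent at drainage: "Once eligibility for study inclusion is determined at the time of drainage". C.1 (Antibiotic regimen) repeats the order: "After percutaneous drainage of the abscess, the patient will be randomly assigned to receive either an 8-day regimen" or the 4-day one. C.1 (Screening) admits two kinds of child, those whose abscess forms "while still in hospital or discharged and then readmitted with abscess".

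**Antibiotic exposure.** Later in C.1 the plan states that "The randomized trial should control for all confounding effects". It then adds that antibiotic treatment before, around and after the operation will be collected, with the "number of days on antibiotic therapy prior to discharge to manage this potential confounder" post hoc. It names no method for managing it and no cut-off at drainage or randomisation.

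**What happens after drainage.** C.1 (Antibiotic regimen) has children on IV treatment until afebrile and eating for 24 hours. It lets the assigned course be finished in hospital or at home, and leaves extension for a child still febrile at course end to the surgeon.

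**Analysis.** C.4 plans simple tests: "Differences among treatment cohorts and on clinical outcomes will be assessed using parametric and non-parametric tests as appropriate". It also plans a model: "Adjusted odds ratios will be used to compare differences among study cohorts and covariates", giving age, gender, white cell count and BMI as examples, together with "interactions, and confounders as appropriate". Confounders are to be found from prior research and empirically by association.

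**The concern.** A confounder of a randomised comparison has to precede assignment. Antibiotic exposure before drainage does, and is a legitimate covariate. Inpatient antibiotic days after drainage do not: they partly record the treatment received and partly how fast the child recovered.

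Take a child who stays 6 days after drainage and is not extended. In the 4-day arm the record shows 4 inpatient antibiotic days; in the 8-day arm it shows 6. So children recorded at 4 days include, in the 4-day arm, some who stayed longer, while in the 8-day arm they stayed about 4 days. If longer stay goes with more readmission, a model that holds this variable fixed compares sicker children on 4 days with less sick children on 8 days. The adjusted odds ratio then departs from 1 with no treatment effect, to the disadvantage of the 4-day arm.

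C.1 has already labelled the variable a potential confounder, and empirical screening as described in C.4 could select it. In an equivalence trial the estimate and its interval are the result, so even a modest artificial shift is unwelcome.

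**Working it through.** **1. The plan's own figure.** The sample size reproduces as two one-sided tests at 0.05 with 10% readmission in each arm, a 10-point margin and 80% power (beta split over the two tests): n = 2 × 0.10 × 0.90 × (1.645 + 1.282)² / 0.10² = 154.1, so 155 per arm; 155 × 1.10 = 170.5, so 171 per arm and 342 in total. No covariate enters this, so the point below does not alter it.

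**2. Which days follow randomisation.**

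- Abscess formed in hospital: drainage and randomisation come before discharge, so days before discharge include days of the assigned course.
- Discharged, then readmitted with abscess: discharge could mean the appendectomy discharge (all before randomisation) or the discharge after drainage (partly after it). The text does not say.

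**3. Size if post-drainage days are adjusted for.** From the documents: courses of 4 and 8 days, 10% readmission in both arms, 10-point accepted difference. Assumed, because the documents give none of them:

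- severity U is standard normal;
- post-drainage stay is log-normal, log-SD 0.5, median 3 to 6 days;
- four severity settings (correlation of log-stay with U / readmission log-odds per SD of U): weak 0.3/0.3, mild 0.5/0.5, moderate 0.7/0.7, strong 0.7/1.0;
- a random share of those still in hospital at course end is extended.

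Inpatient antibiotic days = min(stay, assigned course), or the whole stay if extended. The model is logistic: readmission on arm plus this variable, in a large sample with the same children in both arms and no true effect. Odds ratio, 4-day against 8-day, half extended:

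| Median stay | Weak | Mild | Moderate | Strong |
|---|---|---|---|---|
| 3 days | 1.01 | 1.03 | 1.07 | 1.11 |
| 4 days | 1.02 | 1.05 | 1.10 | 1.14 |
| 5 days | 1.02 | 1.06 | 1.11 | 1.14 |
| 6 days | 1.02 | 1.06 | 1.10 | 1.14 |

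The standardised risk difference runs from +0.1 to +1.2 points. The top of the range is 1.14 or 1.15 depending on the random draws.

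Other settings:

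- 80% extended: 1.00-1.05, at most +0.4 points. All extended: 1.00.
- Pre-drainage plus inpatient post-drainage days as one variable (pre-drainage days assumed to be 5 + N(0, 2) + U, floored at 0), half extended: 1.01-1.13.
- Link reversed (longer-staying children readmitted less often), median 5 days, half extended: 0.83-0.98, a shift of -0.2 to -1.7 points.
- Pre-drainage days alone: 1.00.

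The mechanism shows in mean inpatient antibiotic days at a 5-day median, 4-day against 8-day arm: 4.7 and 5.4 with half extended, 5.3 and 5.6 with 80%, equal with all.

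**4. Sensitivity to the model.** Stay taken as roughly normal in whole days (means 3, 4 and 6), a strong link (log-odds 1.0 per SD) and half extended give 1.12, 1.17 and 1.27, or 1.0, 1.3 and 2.1 points. With no link between severity and stay the shift is about zero.

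**5. Power.** With 171 × 0.9 = 154 per arm, a 5-day median and half extended, the chance that a 90% interval lies within ±10 points (an assumed test), unadjusted then adjusted, is 0.80 and 0.79 (mild), 0.80 and 0.78 (moderate), 0.79 and 0.77 (strong). The loss is 1 to 2 points.

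**The case against.** Several stronger readings are tempting, and the documents do not support them.

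- **That C.1 knowingly combines exposure before and after drainage.** Its wording is pre-, peri- and post-operative, and the operation is the appendectomy. Running past drainage is an inference, secure for abscesses formed in hospital and uncertain for readmitted children.
- **That the plan will adjust the arm comparison for these days.** Managing a confounder post hoc could mean description, stratification or a sensitivity analysis. C.4 includes confounders only where appropriate, and none of its four examples is an antibiotic measure. The data collection form that lists the variables is not among the documents.
- **That the trial's result is biased.** The comparison by arm without adjustment is untouched. C.4 does not say which analysis is primary, but that is a separate matter.
- **That the bias is large.** Assuming nobody is extended takes the odds ratio as high as 2.59. That fits C.1 poorly, because it keeps children on IV treatment until afebrile and eating and allows extension. Since extension is discretionary, full continuation is not assured either.

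These points stand, and they limit the finding to something minor. They do not remove it: C.1 calls a variable that can follow from assignment a confounder, and nothing in C.4 keeps it out of the adjusted comparison.

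**Conclusion.** The point holds as a minor one. C.1 does not separate antibiotic exposure before randomisation from exposure after it, and C.4 leaves the second eligible for adjustment. The reasoning rests on the text alone; the size rests on assumed stay, severity link and extension rate. Under the main model the artificial shift is about 1.2 points at most with half extended, smaller as more are extended, and absent if all are. The alternative model in step 4 reaches 2.1 points. All of these are small beside the 10-point accepted difference. The direction depends on whether longer-staying children are readmitted more or less often, which the documents do not tell us.

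**What to change.** In C.1, limit the potential confounder to antibiotic exposure before drainage, counting any earlier admission. In C.4, add two statements: adjusted comparisons of the arms use only variables fixed before randomisation, of which pre-drainage antibiotic days may be one; and post-drainage antibiotic days are reported descriptively by arm, as adherence data.

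The cost is wording only, provided the data collection form dates antibiotic exposure relative to drainage; if it does not, that date has to be added. The sample size and treatment of the children do not change, and the investigators can still account for earlier antibiotics.

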PROTOCOL

PROTOCOL TITLE	A prospective randomized trial of antibiotic duration in post-appendectomy abscess
PROTOCOL NUMBER	17-055
STUDY DESIGN (PHASE)	Prospective randomized
PROTOCOL VERSION	Version 5 Dated September 25, 2019
NCT NUMBER	NCT03795194
SPONSOR	[name] Phoenix Children's Hospital [name]
PRINCIPAL INVESTIGATOR	[name]

IRB#: 17-055

Title: A prospective randomized trial of antibiotic duration in post-appendectomy abscess

PI: [name]

Col's: [name], [name]; [name]; [name]; [name]; [name]; [name]; [name] [name]; [name]; [name].

Abstract

Appendicitis is a very common surgical problem in children. Although the rates of post-appendectomy abscess in simple appendicitis are less than 1%, the rates of post-appendectomy abscess in complicated appendicitis are not well-described.⁵⁻⁸ Complicated appendicitis includes patients who present with a visible perforation and/or feces in the abdomen, a primary abscess, phlegmon, gangrene, or all of the above.²⁻⁴ Research suggests that neither the type of the antibiotic therapy nor duration of treatment has a significant impact on reducing the risk of post-operative abscess for patients who present with any form of complicated appendicitis.⁷ However, the lack of an evidence-based definition of perforated appendicitis has undermined the reliability of most research results because the study populations may have included non-complicated patients. In this study, we propose to assess the equivalence of an 8-day fixed course and a fixed 4-day course of antibiotics at drainage for perforated patients who develop a post-surgical abscess. We are proposing to study 342 pediatric patients (includes 10% oversampled) ages 2 to 17 years at institutions in the Western Surgical Pediatric Research Consortium (WSPRC) who are diagnosed with perforated appendicitis, treated laparoscopically, **and form an abscess post-laparoscopy**. We hypothesize that the 8-day course of antibiotics is equivalent to the 4-day course on the primary clinical outcome (i.e., readmission rate) and secondary outcomes: length of stay (LOS) upon readmission; rate of abscess from drainage until 30 days after discharge, and wound infection from drainage until 30 days of discharge. This research will provide an ongoing contribution to the clinical management of complicated pediatric appendicitis and antibiotic stewardship.

A. Introduction/Background

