The central hypothesis tested in this study is whether a 4-day antibiotics course is equivalent to an 8-day course for post-drainage primary and secondary clinical outcomes.

Primary outcomes:

- readmission rate

Secondary Outcomes:

- length of stay (LOS)
- rate of post-drainage surgical site infection until 30 days after discharge
- rate of post-drainage abdominal abscess until 30 days after discharge
- secondary site infections

C. Methods

C.1. Study Design

This research proposes a randomized, prospective, equivalence trial design to test the research hypothesis. This study will demonstrate no difference in clinical outcomes between the 4-day antibiotic course and the 8-day course. The study will include 342

IRB#: 17-055

Title: A prospective randomized trial of antibiotic duration in post-appendectomy abscess

PI: [name]

Col's: [name], [name]; [name]; [name]; [name]; [name]; [name]; [name] [name]; [name]; [name].

pediatric patients (includes 10% oversampled) ages 2 through 17 years treated from February 1, 2019 onward until the study cohorts have been filled. This study is based on an expectation of 90% success (10% readmitted) in arm A=10% and expectation of 90% success (10% readmitted) in arm B =10%. The clinical difference in primary outcome between the two groups that we are prepared to accept is equal or greater than 10% (i.e., clinically, we are willing to accept 10 children per 100 who may have benefited from the long course but received a short course to achieve 90% of children who received the short course and would not have benefitted from a long course). The sample size needed to attain a power of 0.80 at alpha=0.05 is 342 (171 in each arm, which includes a 10% attrition rate). The risk of type I error is 1-0.95 (alpha=0.05); power=0.80. The study will proceed until 171 patients are consented for each arm. Study personnel will perform an interim analysis of the data approximately halfway through study enrollment.

Definition of perforated appendicitis - Perforated appendicitis is defined as a visible hole or feces found in the abdomen at laparoscopy. ***For purposes of research, either the hole or feces is photographed, and "hole," "feces/stool in the abdomen," or other note describing perforation will need to be specifically described in the operative report.***

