There will be no direct patient benefit from this study. This research will benefit clinical management by evaluating whether patients achieve significant differences in primary and secondary clinical outcomes based on duration of antibiotic treatment at abscess drainage. The study results may help lower costs for post-appendectomy patient care, improve infection management, and contribute to antibiotic stewardship.

E. Confidentiality and Protection of Human Subjects

E.1. Data Protection, Privacy, Storage, and Security

In accordance with standards for human subjects review, the research study team will adhere to precautions to protect participant privacy and confidentiality of information. Trauma Research will hold the master key of participant names and unique identifiers for use in tracking cases, connecting to data from electronic health records (EHRs), and de-identifying data. All data will be collected by Trauma Research, de-identified, and entered into an encrypted, cloud-based, HIPAA-compliant server (REDCap). Trauma Research will access the data through the website and download to a secure, password-protected network drive at PCH for storage and analysis.

Identifiable patient information will be retained only for as long as the data can be cleaned, verified, and prepped for data analysis. De-identified data will be maintained for up to three months after acceptance of the first scholarly journal article or until study closure, whichever comes first. For data identified for disposal, appropriate measures will be taken; electronic data will be deleted from office computers and the primary location of storage in the network drive, and hard copies containing data will be shredded and disposed of in accordance with PCH policy.

IRB#: 17-055

Title: A prospective randomized trial of antibiotic duration in post-appendectomy abscess

PI: [name]

Col's: [name], [name]; [name]; [name]; [name]; [name]; [name]; [name] [name]; [name]; [name].

E.2. Standard of Care, Confidentiality, and Privacy

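### Equivalence is hypothesised for length of stay with no margin, no single definition and no stated direction of benefit

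*Combined protocol and SAP*

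**What the plan says.** - **Hypothesis.** Section B says that the central hypothesis "is whether a 4-day antibiotics course is equivalent to an 8-day course for post-drainage primary and secondary clinical outcomes", and lists LOS as a secondary outcome. C.1 adds: "This study will demonstrate no difference in clinical outcomes between the 4-day antibiotic course and the 8-day course".
- **Margin and test.** C.1 gives one margin, 10 percentage points, for readmission. C.4 assesses differences at a two-sided alpha of 0.05 with a Bonferroni correction. Neither section gives a margin, standard deviation, power or direction of benefit for LOS.
- **Definition of LOS.** The Abstract has "secondary outcomes: length of stay (LOS) upon readmission". Section B does not say which stay is meant. C.4 lists the stay following drainage as a recovery descriptor and lists LOS again, unspecified, as a secondary outcome.
- **Discharge.** Under the antibiotic regimen in C.1, in-patient treatment continues until the child is afebrile and has tolerated food for 24 hours, in both arms. "A prescribed oral course of antibiotics may be finished in the hospital or at home if patient is discharged". The notes to Diagram 1 also allow discharge before either course is complete.
- **Complications.** C.1 includes all complications in the follow-up and gives a list taken from an external quality programme. Item (2) is abscess; item (5) is "5) length of hospital stay of greater than 4 days".
- **Hoped-for gain.** D.2: "The study results may help lower costs for post-appendectomy patient care".

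**The concern.** An equivalence hypothesis needs a margin and a test that can reject non-equivalence. For LOS the plan has neither, so a non-significant difference would probably be read as equivalence.

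For LOS, two-sided equivalence is also an odd aim. Fewer hospital days with the short course would be welcome and are an obvious route to lower cost, though D.2 does not mention stay. Under the hypothesis as worded, that result is a departure from no difference, and the plan does not say whether it counts for or against the short course.

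Because the stay itself is not pinned down, two analysts could follow the protocol and report different quantities in different sets of children. Item (5) adds a second, dichotomised version of LOS, labelled a complication.

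**Working it through.** **1. What the margin covers.** Inputs from C.1: 10% readmitted in each arm, margin 10 points, alpha 0.05, power 0.80, 10% attrition. The protocol names no formula. Two one-sided tests for two proportions, each at 0.05, reproduce its figure:

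n = 2p(1−p)(z₀.₉₅ + z₀.₉₀)² / margin² = 2 × 0.10 × 0.90 × (1.645 + 1.282)² / 0.10² = 154.1, so 155 per arm.

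155 × 1.10 = 170.5, so 171 per arm and 342 in total, as stated. The calculation concerns readmission only.

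**2. What the C.4 test can say about LOS.** A two-sided difference test has two results.
- *Significant, shorter stay with 4 days:* a departure from no difference, although arguably a benefit.
- *Not significant:* no evidence of equivalence, because no margin has been excluded. The Bonferroni correction makes this result more likely, so it makes a mistaken reading of equivalence easier.

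Neither result supports equivalence.

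To show the precision available, assume an LOS standard deviation of 2 to 5 days (not in the documents) and 155 children per arm. The standard error is SD × √(2/155) = 0.1136 × SD, or 0.23 to 0.57 days. The 95% interval is then about ±0.45 to ±1.11 days (1.96 × SE). Without a margin, nobody can say whether that is narrow enough for equivalence. As a plain estimate of a difference it is usable.

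**3. Which stay, and in whom.**

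| Place | Stay named | Children contributing |
|---|---|---|
| Abstract | on readmission | only those readmitted, if a later readmission is meant |
| B | not specified | not specified |
| C.4, recovery descriptor | following drainage | all randomised |
| C.4, secondary outcome | not specified | not specified |

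At the C.1 rate, a later readmission gives 0.10 × 342 = 34 children, about 17 per arm (0.10 × 310 = 31 if 155 per arm are evaluable). Readmission is the primary outcome and happens after randomisation, so the two groups of readmitted children are no longer a randomised comparison. The Abstract's term is itself ambiguous: under Screening in C.1, some children have already been readmitted with the abscess when they are drained.

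**4. How far assignment could move the stay.** Let f be the share of children, equal in both arms, who are kept in only to finish the course. Each such child stays at most 8 − 4 = 4 days longer in the 8-day arm, so the difference in mean stay is at most 4f days: 0 at f = 0, 1 at f = 0.25, 2 at f = 0.5, 4 at f = 1. The documents give no value for f, and the common discharge criteria are compatible with f = 0.

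**5. Item (5).** It does not say whether the 4 days run from first admission, drainage or a later readmission. It repeats LOS as a yes/no item. Its 4-day cut-off is the experimental course length, so if the days run from drainage and some children are kept in to finish, it can differ by arm for that reason alone.

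**The case against.** The strongest reply is that the plan contains no LOS equivalence test to go wrong. C.4 uses two-sided difference tests, which would show a shorter stay. Stay following drainage is already among the items to be described, and D.2 speaks of evaluating whether outcomes differ. This stands as far as it goes: the data and a usable test are there. It does not remove the mismatch between that test and the hypothesis in B, or the missing definition and direction.

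Three stronger readings are tempting, and the documents do not support them.
- *The assigned course sets the length of stay.* The discharge criteria are the same in both arms, and the sentence that allows the course to be finished in hospital also allows it to be finished at home. A child may finish in hospital simply because the criteria are not yet met. Assignment can lengthen the stay only for a child kept in to finish, and nothing says that any will be.
- *A shorter stay would refute the hypothesis.* With no LOS margin, the plan has no rule by which LOS could confirm or refute anything. The most that can be said is that such a result would count against the wording.
- *Complication rates would be close to universal, since every child enters with an abscess.* No complication count or composite is a named outcome, and the follow-up concerns children who return within 30 days of discharge. The abscess and infection outcomes in the Abstract and the abscess and surgical-site outcomes in B are already limited to events after drainage. Item (2) needs only a clarifying phrase.

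**Conclusion.** The point holds as a defect in how a secondary outcome is specified. The plan cannot support an equivalence claim on LOS, because its only margin is for readmission and its test is for a difference. It names LOS inconsistently and does not say that a shorter stay is a benefit. On one reading of the Abstract, LOS would be compared in about 34 of 342 children selected after randomisation; that figure rests on the protocol's own 10% readmission rate.

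The mechanical effect of course length on stay lies between 0 and 4f days, with f unknown, so no size or power for it can be taken from the documents. Item (5) is undefined in time and redundant, but it has no stated analysis.

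Severity is low. The primary outcome, its margin and the sample size of 342 are unaffected.

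**What to change.** 1. In the Abstract and B (and the matching sentence in C.1), limit the equivalence claim to readmission.
2. Define LOS once, in the Abstract, B and C.4, as the time from drainage to first discharge in all randomised children. Report the between-arm difference with a 95% confidence interval, and state that a shorter stay counts as benefit. Any stay on a later readmission can be described separately.
3. In C.1, remove item (5) from the complications counted in follow-up, since LOS is already an outcome. State that item (2) means abscess after drainage, in line with B.

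The cost is wording in the Abstract, B, C.1 and C.4. C.3 already collects LOS and the duration of each re-hospitalisation, and C.4 already lists stay following drainage, so no patients or data are added. No treatment or discharge rule changes. The downside is that the trial gives up a formal equivalence claim on its secondary outcomes, a claim that the present plan could not have supported for LOS.
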